4.10.1.1 Multi-center Studies

This study is conducted in many sites, and the randomization was not initially stratified by site. After 128 patients were randomised, a new randomisation scheme with stratification by site was put in place to ease the treatment supply on site. Randomisation was balanced by site to allow the clinical supplies team to better predict the required material types and make them available at each site before a patient is randomised.

For the primary efficacy variable, the statistical models to be used for the estimation of dose-response relationship will adjust for differences between centers, by including 'Center' as a main effects term in the model. Adjustment for center will also be performed, wherever possible, in the analysis of the secondary efficacy variables.

Pooling will be applied to deal with small centers. Countries with less than 20 patients will be grouped. The term 'Center' will be used to define the resulting pseudo-centers, for the summaries and analyses.

Descriptive summaries of primary efficacy variable data by treatment group and center will be provided.

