4.10.1.2 Adjustments for Covariates

The primary efficacy analysis will be adjusted for the following baseline covariates:

1. Center
2. Erosive esophagitis due to GERD LA grade C or D, erosive esophagitis due to GERD LA grade A or B who are partial responders to PPI treatment

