4.10.2 Primary Efficacy Variable(s)

Upper endoscopy for the examination of esophagus will be performed to confirm patient eligibility as well as the primary endpoint. The endoscopy examinations will be recorded on a video shot/digital images and these endoscopy videos/digital images will be evaluated by Investigator or endoscopy specialist, as required. Grade of erosive esophagitis due to GERD will be determined by the appropriately trained Investigator or endoscopist according to the LA classification (see Appendix 8 of protocol).

The endoscopy videos/digital images will be collected into a central database, with the appropriate anonymization. All videos and digital images will be centrally reviewed retrospectively. This review will include reassessment of the LA grading and other findings which may constitute exclusion criterion. The central reading evaluation will override the investigators' evaluations and will be used for all reporting and modelling. In case central reading evaluation is missing for a patient at screening or at week 4, due to poor video quality for example, the investigators' evaluations will replace the missing central reading. Hereafter, analyses based on central reading will consider central readings with imputations of local readings if missing.

Data obtained from patients deemed to have been ineligible for study enrollment following the retrospective analysis will be excluded from the per protocol analysis.

In the FAS analysis, the following subgroups of patients will be evaluated:

- the subgroup of patients classified as erosive with grade A/B or C/D at screening according to central reading
- the subgroup of patients classified as non-erosive (grade 0) at screening according to central reading.

A sensitivity analysis will also be conducted to present the healing results based on investigator or endoscopy specialist assessments (local reading). A second sensitivity analysis will be presented by category of LA Grade as assessed by the investigator and reclassified by central reading.

The primary objective of the study is to support dose selection for X842, through assessment of healing of erosive esophagitis due to GERD based on endoscopic assessment after 4 weeks of treatment. The aim is to identify the dose that will lead to having 85% of the patients have esophageal mucosa healing after 4 weeks of treatment.

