Comparison of different doses of X842 to the active comparator arm (lansoprazole 30 mg) will not involve any formal statistical testing.

Lansoprazole treatment group will be analyzed descriptively.

The primary analysis will be performed for both the FAS and PPS as defined in Section 4.5.

In addition, the two subgroups, erosive esophagitis due to GERD LA grade C or D and erosive esophagitis due to GERD LA grade A or B, will be evaluated separately.

In the subgroup of patients with LA grade A or B, some of them were classified as A or B by investigator and thus are partial responders to PPI, but some of them were initially classified as C or D by investigator, and thus may not be partial responders to PPI. A subgroup analysis will be performed on the subgroup of patients with LA grade A/B according to their history of PPI treatment.

The rate of esophageal mucosa healing in the four X842 dose groups after 4 weeks of treatment (endoscopy performed at Visit 5) will be derived using the LA grading of GERD. If the grading is neither A, B, C or D, then the patient will be considered as having esophageal mucosa healing.

The rate of esophageal mucosa healing will be accompanied by 95% Clopper Pearson CI.

The primary analysis will involve dose-response modeling, evaluating a sequence of dose-response models for the healing rate including the Linear, Exponential, E_{max} , Sigmoid E_{max} and Logistic models (on logit scale).

The models will be compared in terms of model fit, and the target dose estimated as the dose providing the target effect of 85% healing rate from the best fitting model will be derived.

Several dose-response models will be fitted with the following factors:

- randomized study treatment (X842 25mg, X842 50mg, X842 75mg and X842 100mg)
- erosive esophagitis due to GERD (LA grade C or D / LA grade A or B)
- Center

Dose-Response Modeling

Multiple Comparison Procedure – Modeling

For all patients assigned to FAS, dose-response modeling will be performed using the multiple comparison procedure – modeling (MCP-Mod) approach [2, 3] with the following models in consideration:

1. Emax: $f(d) = E_0 + E_{max}d/(ED_{50} + d)$.
2. Sigmoidal Emax with $h = 3.5$: $f(d) = E_0 + E_{max}d^{3.5}/(ED_{50}^{3.5} + d^{3.5})$.
3. Logistic: $f(d) = E_0 + E_{max}/\exp((ED_{50} - d)/\delta)$.
4. Exponential: $f(d) = E_0 + E_1 \exp\left(\frac{d}{\delta}\right)$.
5. Linear: $f(d) = E_0 + \beta * d$.

Where:

- d is the dose level,

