- ED_{50} the dose that gives 50 percent of the maximum effect,
- h the Hill coefficient,
- δ the rate of change for the logistic and exponential models,
- β is the slope for linear model,
- E_0 the basal effect at $d = 0$ and
- E_1 the scale parameter in the exponential model.

In the MCP-Mod approach, all statistically significant models listed above will be averaged in order to estimate the median dose for a given targeted response via inverse prediction along with associated 95% intervals using a bootstrap re-sampling method.

For the contrast test the following guesstimates will be assumed.

Model	Guesstimate
Emax	ED50 = 50
SigEmax1	ED50 = 50
Logistic, Exponential	$\delta = 200$

This MCP-Mod analysis will be performed using the R software (“DoseFinding” and “ggplot2” packages) [5], as follows:

1. MCP step:
 - a. Logistic regression model on the response variable with dose levels as categorical to obtain coefficients estimate and the relative covariance matrix.
 - b. “Mod” function of the “DoseFinding” package to perform the multiple contrast test (function “MCTtest”) part on the pre-specified candidate models
 - c. Significant candidate models will be evaluated by t-Test statistic and the adjusted p-value. Candidates for the modeling part will be selected with the following criteria:
 - i. Take the most significant candidate model ($p < 0.05$) or models if the t-Test statistic is equal.
 - ii. Stop if any of the model has not signal ($p > 0.05$).
2. Modeling step (Bootstrap):
 - a. $N = 1,000$ bootstrap samples of dose responses will be generated by a multivariate normal distribution with vector mean equal to the logit coefficients estimated on the MCP step and covariance matrix as its coefficients related covariance matrix.
 - b. For each Sample:
 - i. Fit the model by the “fitMod” function and select the best with goodness of fit based on the AIC criteria.
 - ii. Prediction of response probabilities based on the best model.
 - iii. Save the predicted values.
3. Compute the median of the bootstrap predicted values and 95% CIs.
4. Extraction of the dose at the target response probability with 95% CI.

Should there be three or more candidate model fail to fit on a bootstrap sample, the estimate for the bootstrap sample will be taken as unreliable. In case less than 70% of bootstrap sample estimates are taken as reliable an additional generalized linear mixed model (GLMM) analysis will be performed as

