4.5 Efficacy Analyses

4.5.1 Analysis and data conventions

4.5.1.1 Adjustment for covariates

The primary efficacy dose – response model analysis will be adjusted for the following baseline covariates, where the second covariate is modified compared to the original SAP.

1. Center
2. Erosive esophagitis due to GERD LA grade C/D, erosive esophagitis due to GERD LA grade A/B ~~who are partial responders to PPI treatment.~~

The modification is an adjustment to the included LA grade A/B patients without history of partial response to PPI treatment. In analysis datasets FAS erosive PR and PPS, patients who are not partial responders to PPI treatment are not included, and hence the covariate adjustment will effectively follow the original SAP and the original intention of the objective.

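### The primary dose-response model must adjust for LA grade and centre, but the steps that extract the 85% dose state no coding and no averaging over patients, so that dose is not tied to 85% of patients healing

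*SAP*

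**What the plan says.** **Target.** SAP 4.10.2 sets a population proportion as the goal: "The aim is to identify the dose that will lead to having 85% of the patients have esophageal mucosa healing" after 4 weeks.

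**Adjustment.** Four places call for covariates.
- SAP 4.10.1.1: "the statistical models to be used for the estimation of dose-response relationship will adjust for differences between centers", with Center as a main effect.
- SAP 4.10.1.2: "The primary efficacy analysis will be adjusted for the following baseline covariates", namely Center and LA-grade group.
- SAP 4.10.2: "Several dose-response models will be fitted with the following factors", listing dose arm, LA-grade group and Center.
- SAP amendment 4.5.1.1, on the primary dose-response analysis: it "will be adjusted for the following baseline covariates, where the second covariate is modified compared to the original SAP". It keeps Center and LA grade.

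**Algorithm.** The numbered steps in SAP 4.10.2 are worded differently. Step 1a is a "Logistic regression model on the response variable with dose levels as categorical to obtain coefficients estimate and the relative covariance matrix", with no covariate named. Step 2a draws from a "multivariate normal distribution with vector mean equal to the logit coefficients estimated on the MCP step". Each draw is fitted on the logit scale and converted to response probabilities, and step 4 is "Extraction of the dose at the target response probability with 95% CI". No step gives a reference level, a contrast coding, covariate values for prediction, or averaging over patients. Least squares means appear only in the fallback mixed model, which yields rates per arm and no target dose.

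**Analysis sets.** These are named: FAS erosive as primary and PPS as supportive (SAP 4.10.2 output list; amendment 4.5.2).

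**The concern.** In a logistic model with covariates, a dose logit is the log-odds of healing at some covariate profile. Which profile depends on coding: a reference grade and centre, or an artificial mean profile under sum-to-zero coding. Converting such a logit to a probability does not return the proportion healed among the trial's patients. A dose read off at 85% is therefore conditional on an unstated choice, while the stated aim is a population proportion.

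The 85% dose is the main output of the primary analysis, and SAP 4.10.1 sets good precision as the objective. Two things are at stake. The labelled dose may heal more or fewer than 85% of patients. Its interval may also be wider than it need be, because under reference coding it carries the uncertainty of one grade and one centre.

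**Working it through.** The documents give no 85% dose, LA effect, centre effect or slope to reproduce, and the sample-size sections are redacted. All effect sizes below are assumptions. The inputs from the documents are the 85% target (SAP 4.10.2), 48 patients per arm and an LA mix of about 50:50 (protocol 6.3.1). Central reading reclassifies grades (SAP 4.10.2), so the analysed mix may differ from 50:50.

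**1. True healing at the dose labelled 85%.** Let T = logit(0.85) = 1.735, g = ln(OR) for A/B versus C/D, and p = the share of A/B. There is no centre effect here. Population healing = p·expit(a) + (1−p)·expit(c), where (a, c) is
- A/B reference: (T, T−g)
- C/D reference: (T+g, T)
- equal weight: (T+g/2, T−g/2)

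For OR = 2 and p = 0.5, on the odds scale (0.85/0.15 = 5.667):
- A/B reference: C/D odds 2.833, so 73.9%; mean of 85.0 and 73.9 = 79.5%
- C/D reference: A/B odds 11.33, so 91.9%; mean of 91.9 and 85.0 = 88.4%
- equal weight: odds 8.014 and 4.007, so 88.9% and 80.0%; mean 84.5%

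| Assumed OR | A/B reference, 50:50 | C/D reference, 50:50 | Equal weight, 50:50 | Equal weight, 30% or 70% A/B |
|---|---|---|---|---|
| 1.5 | 82.0% | 87.2% | 84.8% | 83.8% or 85.9% |
| 2 | 79.5% | 88.4% | 84.5% | 82.7% or 86.2% |
| 3 | 75.2% | 89.7% | 83.7% | 80.8% or 86.5% |

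If C/D patients healed better than A/B, the two reference columns would swap. With five equal centres added (logit SD 0.3, OR 2), the extremes of reference coding are 71.2% (A/B, best centre) and 91.9% (C/D, worst centre).

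**2. Precision when the covariates do nothing.** Take healing of 85% at 60 mg, slope 0.03 per mg, OR 1, no centre effect, and K equal centres balanced over arms and grades. The information per arm is I = 48·P(1−P), where P is healing in that arm: 10.69, 7.46, 4.36 and 2.30 at 25, 50, 75 and 100 mg, total W = 24.8. For a dose logit at a reference profile,

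variance = 1/I + K/W,

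where LA grade adds 1/W and Center adds (K−1)/W. At 25 mg the standard error without covariates is √(1/10.69) = 0.31. With five centres it is √(0.0935 + 5/24.8) = 0.54. Under equal weighting in this balanced case it stays at 0.31.

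**3. Dose scale, illustration only.** Steps 2a to 4 were simulated with Center in step 1a, a true 85% dose of 60 mg, slope 0.03, centre SD 0.3 and OR 2. Median extracted doses were 61 mg standardised over patients, 56 mg equal weight, 44.5 mg A/B with the middle centre and 70 mg C/D with the middle centre. The standardised 10–90% half-width was 12 to 15 mg across settings. With no LA or centre effect and five centres, the 10–90% range was 46 to 73 mg standardised, against 32 to 81 mg (A/B reference) and 31 to 88 mg (C/D reference). The run was not the exact SAP procedure: no significance gate, 200 draws instead of 1,000, grid fitting instead of fitMod, the standard logistic form, and a penalised fit where a group had 0% or 100% healing.

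**4. Contrast test.** Changing the reference profile adds the same amount to all four dose logits. Contrast weights sum to zero, so that amount cancels.

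**The case against.** The strongest reply is that step 1a is the operational text and names dose alone. Run that way, the four logits are arm-level and the problem disappears; a dose-only fit in the simulations gave medians of 60 to 62 mg against a true 60 mg. A reader might infer that the SAP definitely reads the dose at one LA-grade and centre profile. The documents do not support that. They show an inconsistency between the factor list and step 1a, and the single-profile result also needs reference-level coding, which is nowhere stated. What survives is that four passages require adjustment, one of them in the amendment and specific to this model, so the dose-only reading contradicts the plan.

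Second, equal-weight or sum-to-zero coding does little damage near a 50:50 mix. This is correct, but the SAP does not specify it, and the error grows if central reading moves the mix.

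Third, a reader might take the mg shifts as the error to expect in this trial. They depend on assumed effects and an approximate procedure. Against a 95% half-width (12 to 15 mg × 1.96/1.28, about 18 to 23 mg), the OR 2 shifts of about 16 mg (A/B) and 9 mg (C/D) lie inside.

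Fourth, a reader might infer that SAS and R programs would disagree, since SAP 4.3 plans SAS outputs with R for quality control. Nothing shows two differently coded programs, and SAP 4.1 requires independent checking.

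Finally, other outputs limit the harm: arm rates with exact intervals, dose-response models by LA grade (SAP 4.10.1.6), and Phase 3 selection that also uses safety and PK (protocol 2.2). They can reveal a mismatch but do not correct the overall 85% dose.

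**Conclusion.** The point holds in conditional form. If LA grade and Center enter step 1a as the SAP and its amendment require, steps 2a to 4 give a dose that depends on unstated coding. Reference-level coding ties it to one profile and makes it less precise even with null covariates. Equal-weight coding leaves a small error near 50:50. Neither yields the dose at which 85% of patients heal, except when the covariates have no effect.

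The illustrative size at OR 2 and 50:50 is about 5.5 points low or 3.4 points high under reference coding and about 0.5 point low under equal weighting. All of this rests on assumed LA and centre effects. The dose-response contrast test is not affected by the reference choice. This should be fixed because it concerns the main output and a better method needs only data already held. It does not show that the reported dose is wrong.

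**What to change.** Reconcile the factor list in SAP 4.10.2 with step 1a by stating that the logistic regression contains categorical dose, LA grade and Center.

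For steps 2a to 4, predict healing for every patient of the named analysis set (FAS erosive, PPS) at each dose, using that patient's observed LA grade and Center. Average the predicted probabilities within dose and take logits of the four standardised rates. Use these with their delta-method or bootstrap covariance in place of the raw coefficients, and state that 85% refers to the standardised rate. Leave the contrast test as planned.

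The SAP amendment was written after unblinding (Section 3) and treats results not defined in the original SAP as explorative (4.3.3). The change should therefore be labelled a post-unblinding clarification, and the result as programmed should be reported beside it with its coding stated.

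The cost is a small amount of programming, with no new data, patients or visits. Handling arms or centres with 0% or 100% healing is a separate implementation point and not part of this change.

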4.10.3 Secondary Efficacy Variables

Analyses of the secondary efficacy endpoints will be performed for the FAS and the PP as defined in Section 4.5.

QOLRAD scores and mRESQ-eD means or proportions will be estimated using a Generalized Linear Mixed Model (GLMM) approach using information of each week for each subject, on observed data, assuming missing at random.

The models will be implemented using all available timepoints (as categorical), the X842 dose level or lansoprazole as covariate and the related interaction, center and erosive esophagitis due to GERD (LA grade C or D / LA grade A or B).

Toeplitz covariance matrix will be assumed. In case of convergence failure, the following matrices will be tested until convergence is reached: 1. Compound Symmetry, 2. Autoregressive 1 (AR-1).

Mean and standard error estimated from the model will be provided in the outputs. Median, Q1, Q3, Min and Max will be reported as observed data.

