2 STUDY OBJECTIVES

Objectives	Endpoints
Primary	
The primary objective of the study is to support dose selection for X842, through assessment of healing of erosive esophagitis due to GERD after 4 weeks of treatment.	Healing of erosive esophagitis due to GERD based on endoscopic assessment after 4 weeks of double-blind treatment.
Secondary	
Evaluate the safety and tolerability of the four dose levels of X842 and lansoprazole, where lansoprazole will serve as the active comparator.	Physical examination, weight, BMI, vital signs, electrocardiogram (ECG) recordings, safety laboratory measurements (hematology/clinical chemistry/urinalysis), adverse event (AE), treatment emergent adverse event (TEAE), adverse event of special interest (AESI), serious adverse event (SAE) reporting, concomitant medication(s).
Evaluate the reflux related symptom pattern during the initial 4 weeks treatment with four dose levels of X842 and with lansoprazole, and the symptom pattern during the subsequent additional 4 weeks (Weeks 5-8) open-label treatment with lansoprazole 30 mg QD.	
 Percentage of heartburn-free 24-hour days during the Weeks 1-8 (Visits 2-9) based on eDiary (mRESQ-eD), including splits into day- and nighttime evaluations Percentage of 24-hour days with at most mild heartburn symptoms during the Weeks 1-8 (Visits 2-9) based on eDiary (mRESQ-eD), including splits into day- and nighttime evaluations Investigator assessment of symptom at Weeks 1-8 (Visits 2-9) Reflux related impact as measured by change from baseline in QOLRAD scores assessed after 1, 2, 4 and 8 weeks of treatment.
Exploratory	
  	  
  	  

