3.2.1.2 Secondary efficacy endpoints

- Percentage of heartburn-free 24-hour days during the Weeks 1-8 based on eDiary (mRESQ-eD).

- Percentage of 24-hour days with at most mild heartburn symptoms during the Weeks 1-8 based on eDiary (mRESQ-eD).
- Investigator assessment of symptom at Weeks 1-8 (Visits 2-9).
- Reflux related impact of symptoms as measured by change from baseline in QOLRAD score assessed after 1, 2, 4 and 8 weeks of treatment.

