4.10.3.1 QOLRAD

Reflux related impact will be assessed based on the patient reported outcome (PRO) QOLRAD. The heartburn version of the QOLRAD is a disease specific instrument and contains 25 questions addressing concerns associated with gastrointestinal symptoms. Each question is scored from 1 to 7, where a higher score represents a higher (“better”) health-related quality of life.

The QOLRAD will be completed pre-dose by patients at Visits 2 (Baseline), 3 (Week 1), 4 (Week 2), 5 (Week 4), and 9 (Week 8) (see Table 1 in section 6.1).

The questions are categorized into five domains: emotional distress (six questions), sleep disturbance (five questions), vitality (three questions), food/drink problems (six questions) and physical/social functioning (five questions).

- Emotional distress (questions 12, 14, 15, 17, 19, 22)
- Sleep disturbance (questions 8, 10, 11, 18, 21)
- Food/drink problems (questions 3, 5, 9, 13, 16, 20)
- Physical/social functioning (questions 2, 6, 23, 24, 25)
- Vitality (questions 1, 4, 7)

For the calculation of domain scores, in case of missing items, these missing items can be replaced under specific conditions (the half-scale method) as follows:

- If 50% or more of the questions in one dimension are completed, the mean value of the completed items should replace the missing responses.

- If less than 50% of the questions in one dimension are completed, the missing responses will not be replaced.

The score in each domain will be calculated as the mean of all items in that domain, only if all items are not missing after replacement.

To evaluate the reflux related impact pattern during the initial 4 weeks treatment and the subsequent additional 4 weeks (Weeks 5-8) open-label treatment with lansoprazole 30 mg QD, the following summaries will be provided by study treatment group and assessment day:

- A summary of QOLRAD domain scores and change from baseline (FAS/PP)
- A plot of QOLRAD domain scores at baseline and Week 1, Week 2, Week 4 and Week 8 (FAS/PP).

A listing of QOLRAD results will be provided. Original values and imputed values will be provided, together with domain scores.

4.10.3.2 mRESQ-eD

Reflux related symptoms will also be assessed based on the modified RESQ-eDiary. mRESQ-eD contains 8 items where 5 items assess severity (Did not have – Severe) and 3 items assess frequency (Never – Very often) of symptoms.

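### The longitudinal model for QOLRAD scores has no baseline QOLRAD term and no common-baseline constraint, so the secondary QOLRAD estimates lose precision and carry chance baseline imbalance

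*SAP*

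**What the plan says.** The SAP defines the secondary endpoint in section 2 as "Reflux related impact as measured by change from baseline in QOLRAD scores assessed after 1, 2, 4 and 8 weeks of treatment"; section 3.2.1.2 says much the same. Section 4.10.3.1 and the schedule of assessments place the questionnaire pre-dose at Visit 2 (labelled baseline) and then at Weeks 1, 2, 4 and 8. The listed outputs, by treatment group and assessment day, are domain scores with change from baseline, and a plot of scores that includes baseline.

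Section 4.10.3 describes the model: "QOLRAD scores and mRESQ-eD means or proportions will be estimated using a Generalized Linear Mixed Model (GLMM) approach", fitted "on observed data, assuming missing at random". Its terms are given as "using all available timepoints (as categorical), the X842 dose level or lansoprazole as covariate and the related interaction, center" and the LA grade group, where the list ends. On correlation between visits it says "Toeplitz covariance matrix will be assumed", with compound symmetry and then AR(1) if the fit does not converge. The model supplies means and standard errors for the outputs.

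Nothing readable elsewhere adds a baseline score. Section 4.10.1.1 adds only centre for secondary variables. Section 4.10.1.2, and its revision in section 4.5.1.1 of the SAP amendment, concern the primary analysis and list only centre and LA grade. Section 4.5.3 of the amendment names analysis sets, not covariates. Section 4.10.1.4 of the SAP plans no formal testing, and protocol section 9.4.7 treats these endpoints as descriptive.

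**The concern.** When the question is change from a measured starting point, that starting value normally belongs in the model. Without it, an arm that happens to start with worse scores tends to show a larger improvement simply through regression to the mean. An arm that starts better tends to look better at follow-up. Adjustment removes most of this and tightens the estimates, using data already scheduled.

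The arms are small enough for chance differences to show: about 48 randomised per arm, or 200/5 = 40 if the 200 evaluable patients divide evenly. They are smaller still in the erosive partial-responder set, which section 4.3.3 of the amendment says has fewer patients than planned. With no hypothesis test, the estimates and their standard errors are the whole product of this analysis.

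What is at stake is the quality of the QOLRAD means, their standard errors and the informal comparison of arms.

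**Working it through.** **Inputs.** From the documents: five arms allocated 1:1:1:1:1, 48 randomised per arm and 40 evaluable per arm by division. The readable text gives no QOLRAD standard deviation, effect size or baseline correlation, and the sample size sections are redacted, so there is no stated figure to reproduce. Two assumptions follow. The baseline-to-follow-up correlation r is taken as 0.3, 0.5 and 0.7. Variances at baseline and follow-up are taken as equal, and results are in SD units. Because centre and LA grade are already in the model, r is the correlation remaining after those terms.

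**Step 1: difference between two arms, n per arm.**
- Post-baseline score, unadjusted: variance 2/n.
- Change score, unadjusted: variance 4(1−r)/n.
- Baseline-adjusted: variance 2(1−r²)/n.

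The adjusted variance is therefore (1+r)/2 of the change-score variance and 1−r² of the post-score variance.

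| r | adjusted/change, variance | SE cut | adjusted/post score, variance | SE cut |
|---|---|---|---|---|
| 0.3 | 0.65 | 19% | 0.91 | 5% |
| 0.5 | 0.75 | 13% | 0.75 | 13% |
| 0.7 | 0.85 | 8% | 0.51 | 29% |

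At n = 40 and r = 0.5, the SE is √(2/40) = 0.224 SD for either unadjusted analysis and √(2×0.75/40) = 0.194 SD adjusted. An unadjusted analysis would need 40/0.75, about 53 per arm, to match.

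**Step 2: one arm's own mean change.** This is closer to what the SAP tabulates. Unadjusted variance is 2(1−r)/n. The adjusted mean change, taken from the overall baseline mean of five equal arms, has variance (1−r²)/n + (1−r)²/(5n). The ratio is (1+r)/2 + (1−r)/10:
- r = 0.3: 0.65 + 0.07 = 0.72, an SE cut of 15%.
- r = 0.5: 0.75 + 0.05 = 0.80, an SE cut of 11%.
- r = 0.7: 0.85 + 0.03 = 0.88, an SE cut of 6%.

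**Step 3: chance imbalance.** The baseline difference between two given arms has SE √(2/n): 0.224 SD at n = 40 and 0.204 SD at n = 48. It exceeds 0.3 SD in size with probability 0.18 and 0.14 respectively. An imbalance of 0.3 SD shifts an unadjusted post-score difference by 0.3r = 0.09, 0.15 or 0.21 SD at the three correlations. It shifts a change-score difference by −0.3(1−r) = −0.21, −0.15 or −0.09 SD.

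**Step 4: does listing Visit 2 among the timepoints solve it?** In 800 simulated trials (five arms of 40, five timepoints including baseline, complete data, known covariance), the model had free arm-by-time means plus centre and LA grade. The correlation between baseline and the visit compared was 0.5. The table gives the SD of the between-arm difference.

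| Covariance | Visit 2 as free timepoint | plain change score | baseline-adjusted |
|---|---|---|---|
| Toeplitz | 0.226 | 0.227 | 0.197 |
| Compound symmetry | 0.229 | 0.231 | 0.201 |

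With a separate baseline mean for each arm, the joint model does essentially no better than the plain change score.

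**The case against.** The strongest reply is that the SAP models scores over all available timepoints, not change. Because the planned plot includes baseline, Visit 2 may well be a modelled timepoint. Baseline then enters the likelihood and helps under missing at random. That is a fair reading, and it means a reader should not infer that the SAP specifies a change-from-baseline model; change is the endpoint and a listed output. It does not remove the loss, because Step 4 shows that free arm-by-time means do not recover it with complete data.

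Other stronger inferences also fail:
- **That the 35% to 15% variance cut applies to the reported arm means.** It applies to between-arm differences. The SAP lists model means and standard errors but no QOLRAD contrast, so for the tabulated mean changes the cut is 28% to 12%.
- **That dose selection is put at risk.** The protocol rationale bases the Phase 3 dose on healing, safety and PK, and the primary target is an 85% healing rate.
- **That the unadjusted estimates are biased.** Randomisation keeps them unbiased over repeated trials. The issue is precision and the imbalance in the one trial that is run.
- **That a baseline exists for every patient.** The schedule asks for one, but under section 4.10.3.1 a domain score stays missing when fewer than half its items are answered.

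It also stands that the size of the gain rests on a correlation that the documents do not give.

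**Conclusion.** The point holds as a modest improvement to a secondary analysis. No baseline QOLRAD term or common-baseline constraint appears in the readable text of the SAP or its amendment, and the loss is present whether the outcome is change, the post-baseline score, or all visits with free arm-by-time means. For r between 0.3 and 0.7 with equal variances, adjustment would lower the variance of a between-arm difference in change by about 35% to 15%, and of an arm's own mean change by about 28% to 12%. The gain over an unadjusted post-baseline score rises with r, the gain over change falls with r, and the SAP does not settle which comparison applies. That lack of definition is part of the finding. The effect is confined to the QOLRAD means, their standard errors and informal comparisons between arms.

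**What to change.** First, state the modelled outcome and whether Visit 2 is one of the modelled timepoints. Then choose one of two forms:

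1. **Preferred:** keep Visit 2 as a response with Weeks 1, 2, 4 and 8, and constrain its mean to be equal across arms. Patients without a baseline domain score stay in the analysis, in line with the SAP's use of observed data.
2. **Alternative:** use Weeks 1, 2, 4 and 8 as responses, with the baseline domain score and its interaction with visit as covariates. This needs a stated rule for missing baselines, since otherwise those patients' later visits drop out. The two forms are not interchangeable when baselines are missing.

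No new data are needed; the cost is a short change to the model and its programming. Because the SAP amendment was itself written after unblinding and treats results not defined in the original SAP as exploratory, an addition at that stage should be labelled post hoc and reported beside the planned model.
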